4.2 Secondary Objectives

The objective of Aim 2 (*Heterogeneity of Treatment Effects*) is to determine whether key factors predict or moderate differential treatment engagement or response, in turn informing treatment personalization for various patient subgroups. To understand heterogeneity in treatment response across youth, moderating factors examined include: demographic factors, clinical factors, caregiver and youth attitudes, and language of care (English versus Spanish). Additional factors are also assessed to afford further tests of predictors and moderators of treatment response.

Aim 3 (*Implementation Facilitators and Barriers*) is exploratory, with the objective to understand perspectives, preferences, background factors, clinical and treatment engagement variables, and organizational factors that facilitate or impede implementation of, and patient engagement with, the comparators in routine pediatric health settings.

5 – Engagement and Partnerships with Patients, Other Stakeholders, and Scientific Advisors

Throughout all stages of the Kids FACE FEARS trial, investigators are engaged in collaborations with patient, parent, and community stakeholders who have experience (themselves or loved ones) with mental health challenges such as anxiety, as well as with treatment providers, clinical supervisors, and program administrators who are responsible for providing care to families. Investigators also engage with a Study Advisory Committee comprised of members dedicated to improving access to evidence-based treatment, and a Data Safety and Monitoring Board to further ensure patient safety and protection. These mutual partnerships with stakeholder groups meaningfully inform each aspect of the study design, implementation, and dissemination, as described below.

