6.3 Study Population

6.3.1 Number of Participants. Power analysis (accounting for an expected attrition and missing data) indicated we require 150 participants per group, for a total of 300 participants in the study.

6.3.2 Eligibility Criteria. The study eligibility and inclusion, and exclusion criteria for families include:

Inclusion/ Eligibility

- Elevated child/adolescent anxiety - Operationalized as T-Score on the PROMIS Pediatric Short Form-Anxiety Scale v2.0 ≥ 55 (Child eligible if *either* the Pediatric Self-Report *or* the Parent Proxy Report score was ≥ 55)
- Child aged 7-18 years (inclusive) at time of screening
- Child and caregiver(s) are fluent in English or Spanish
- If taking medication for emotional problems, child must be on a stable dose (Operationalized as no adjustments to prescription for ≥ 8 weeks)

Exclusion Criteria

- Severity requiring higher level of care, as defined by any of the following:
 - Suicidal thoughts or behaviors (STB) with *active* plan or STB(s) that required a higher level of care within the past 6 months (e.g., inpatient, partial hospitalization)
 - Anxiety-related absences $\geq 50\%$ of school days over the past month (If summer, attendance during last month of previous school year considered)
 - Substance use that required emergency services or inpatient/partial hospitalization within past 3 months

- Clinician determined child requires higher level of care than outpatient services
- History of diagnosed autism spectrum disorder or intellectual disability with severe challenges and needs for support (e.g., complete absence of verbal communication unrelated to anxiety)
- Currently engaged in CBT or planning to continue different therapy for anxiety during study treatment phase
- Child is a ward of the state

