7.16 Statistical Considerations

Study results will be reported according to CONSORT guidelines.

7.16.1 Sample size determination. Power analysis to determine the appropriate sample size for the trial had to take into account data clustering and repeated measurements. Study data were clustered in multiple ways, resulting in non-independent observations and inflated type I error. First, there were multiple observations per child due to the repeated measures design with four major assessment points. Second, there was additional clustering due to multiple children from each site. The intraclass correlation (ICC) is a quantitative estimate of clustering and allows for adjustment for non-independence. Study investigators estimated an ICC of .5, meaning it was anticipated that 50% of the variation in the observations would be due to differences between individuals and between sites (the remaining 50% of the variation was assumed to be due to individuals varying in their responses over time). The design effect (DE) reflects the extent to which standard errors are deflated if clustering is ignored. The DE is equal to $1 + (m - 1) \times \text{ICC}$, where m is the number of repeated measures. Accordingly, with 4 time points and an assumed ICC of .5, the design effect was calculated to be 2.5. Any sample size estimate must be multiplied by 2.5 in order to obtain a sample size appropriate for the observed clustering while maintaining nominal alpha and power levels.

The required study sample size was calculated via conventional methods for repeated measures / mixed models analysis. Required sample size is a function of the alpha (type I error rate) and beta (1 – power) values. Required size per group is: $n = 2 * (Z_{1-\alpha} + Z_{1-\beta})^2$. Before adjusting for the DE, these computations found $n=60$ was required in each group for an $\alpha=.05$ (assuming family-wise error rates=.05 across the study to account for multiple comparisons) and $\text{power}=.8$ (corresponding to $\beta=.2$). After adjusting for the DE of 2.5, this power analysis indicated $n=150$ was required per group (60×2.5), for a total of $N = 300$.

The needed sample size of $N = 300$ (outlined above) was based on the primary comparative effectiveness tests of this study (Aim I). That said, a sensitivity analysis was also conducted to evaluate the magnitude of effects that could be detected in moderation analyses

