examining heterogeneity of treatment effects (Aim II). These analyses were conducted with G*power using the repeated measures analysis of variance (ANOVA) test. Repeated measures ANOVA is similar to a mixed model in some respects, but simpler and uniformly less powerful⁸⁰ using the repeated measures ANOVA, therefore, offers a conservative estimate of the effects able to be detected with each mixed model. With $N = 300$, $\alpha = .05$, power = .8, two treatment conditions, four measurements, and a correlation between repeated measures of .5, the trial was powered to detect moderation effects as small as Cohen's $d = 0.068$. This is 7% of a SD difference and a very small effect.

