For primary analyses on the dichotomous categorical outcomes PARS Treatment Responder Status at posttreatment, baseline PARS scores will be examined for each participant to determine their individual thresholds for classification as Treatment Responders (i.e., 35% PARS score reduction). These thresholds will be used to classify each participant's statuses as posttreatment. Logistic regression models will examine Treatment Condition (along with the study covariates) as a predictor of Treatment Responder Status and Remission Status at post. For primary analyses on continuous outcomes of Treatment Satisfaction at post, linear regression models will examine Treatment Condition (with the study covariates) as a predictor of caregiver- and youth-reported posttreatment satisfaction.

7.16.5 Heterogeneity of treatment effects. For Aim II analyses (heterogeneity of treatment effects) predictor and moderator terms will be added to the models predicting youth anxiety severity that were outlined above. For study covariates being considered as predictors/moderators (e.g., language of care, youth age, youth gender, youth race, youth ethnicity, and family resource security), this will entail only adding interaction terms, as the main effects of these variables will already be in the models. For the additional variables considered as treatment moderators that are not already included as model covariates (e.g., caregiver nativity) this will entail adding main effects and interaction terms to the models. For each model examining heterogeneity of treatment effects, the relevant terms of interest will be the 2-way interaction of Variable \times Time (reflecting whether the variable uniformly predicted change across the two treatments) and the 3-way interaction of Variable \times Treatment Condition \times Time (reflecting whether the variable moderated treatment effects; i.e., whether the variable predicted differential response across the treatments). As with the Aim I comparative effectiveness analyses, log transformations of Time will be entered to consider non-linear models of change. Significant interactions will be followed up with post-hoc probing on subgroups to clarify the nature and direction of interaction, and results will be plotted for visual depiction.

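### Aim II tests an open list of moderators on two informants with no stated threshold, test family or multiplicity control, so the family-wise rate of .05 assumed in section 7.16.1 is not delivered there

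*Combined protocol and SAP*

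**What the plan says.** **Error rate.** Section 7.16.1 sets alpha at .05 and power at .8, "assuming family-wise error rates=.05 across the study to account for multiple comparisons". The statement sits inside the sample-size calculation, which the same section ties to Aim I. The protocol and SAP name no Bonferroni, Holm or false-discovery procedure, no hierarchy and no test family.

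**Moderation alpha.** The sensitivity analysis for Aim II, also in 7.16.1, uses N = 300, alpha .05, "power = .8, two treatment conditions, four measurements, and a correlation between repeated measures of .5". It concludes that "the trial was powered to detect moderation effects as small as Cohen's" d = 0.068.

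**Moderators.** Section 7.16.5 names six covariates as examples ("language of care, youth age, youth gender, youth race, youth ethnicity, and family resource security") and caregiver nativity as one example of a further variable, which makes seven. Section 4.2 is wider: "moderating factors examined include: demographic factors, clinical factors, caregiver and youth attitudes, and language of care (English versus Spanish"), and then allows additional factors. Section 6.2.2 adds provider, organizational and system characteristics.

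**Tests.** Each variable contributes a Variable × Time term (does it predict change in both arms alike?) and a Variable × Treatment Condition × Time term (does it moderate the treatment effect?). These go into the anxiety severity models, and 7.16.4 runs a separate model for each outcome, with caregiver and youth PROMIS reports as distinct outcomes.

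**Follow-up.** "Significant interactions will be followed up with post-hoc probing on subgroups to clarify the nature and direction of interaction".

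**Status of the aim.** Section 4.2 makes Aim II a secondary objective meant to guide the tailoring of treatment to subgroups. It calls Aim III exploratory but does not say so of Aim II.

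**The concern.** Whatever passes as significant in 7.16.5 becomes a subgroup analysis and a candidate statement about which format suits which families. With no closed list, a reader cannot know how many tests produced a reported moderator. With no threshold or adjustment, a reader of 7.16.1 may take a .05 family-wise rate to cover these tests when nothing in the analysis sections makes it so.

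The named variables include language of care, race, ethnicity and resource insecurity. A chance interaction on one of them could steer such families toward or away from a treatment format. Effects chosen because they crossed a threshold also tend to be overestimated.

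**Working it through.** **1. Reproduce the plan's moderation figure, to see which alpha it used.** Inputs from 7.16.1: N = 300, two groups, m = 4 measurements, correlation ρ = .5, power .8. For the within-between interaction of a repeated-measures ANOVA, the noncentrality is λ = f² × N × m / (1 − ρ), on 3 and 894 degrees of freedom.
- At alpha .05, power .8 needs f = 0.0675, so λ = 0.0675² × 300 × 4 / 0.5 ≈ 10.9. The printed 0.068 reproduces.
- It reproduces as Cohen's f. The corresponding d is 2f = 0.135, so the label d in the plan is wrong.
- At .05/14 = .0036 the same calculation gives f = 0.087. The plan's figure therefore rests on an unadjusted .05.

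**2. Count the tests.** Only the three-way terms bear on who benefits from which format.
- Seven named moderators × 2 informants = 14 tests.
- If clinical factors, caregiver attitudes and youth attitudes (section 4.2) each add just one variable, there are 10 moderators and 20 tests. This count is an assumption; the plan gives no number.
- Each moderator is counted as one test per informant.

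**3. Chance of at least one false three-way finding**, at .05 per test with no true moderator. For k independent tests it is 1 − 0.95^k:
- 7 tests (one informant): 1 − 0.95^7 = 30.2%
- 14 tests: 1 − 0.95^14 = 51.2%
- 20 tests: 1 − 0.95^20 = 64.2%

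**4. Allow for correlation.** Test statistics were simulated as multivariate normal, with assumed correlations of 0 to .3 between moderators and 0 to .7 between informants.

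| Moderators × informants | Independent | Strongest correlation tried (.3 and .7) |
|---|---|---|
| 7 × 2 | 51.2% | 41.5% |
| 10 × 2 | 64.2% | 51.8% |

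With a between-informant correlation of .5 or more, the seven-moderator figure stays below 50% throughout (41.5% to 48.6%).

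**5. Cost of control.** In the plan's own model, power at f = .068 is 81% at alpha .05. Under Bonferroni over 14 tests (alpha .0036) it is 47%. That model is a two-group interaction with time; a true three-way moderator test would have less power than either figure.

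**The case against.** The strongest reply has four parts.

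- **Testing the interaction before looking at subgroups is sound practice.** This stands. The sequence is not the problem. What is missing is the threshold, the list and the family on which it depends.

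- **The .05 family-wise statement is a planning assumption for Aim I, not a commitment for Aim II.** This largely stands. A reader might infer that 7.16.5 flatly contradicts a promised error rate, but the location of the statement does not support that. Its wording does reach across the whole study, however, so it needs to be either implemented or narrowed.

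- **Section 7.16.5 never says p < .05.** Correct. The threshold is inferred from the sensitivity analysis, which is a power calculation and not a decision rule. The accurate criticism is that threshold and adjustment are unspecified; the probabilities above show what follows if .05 is used.

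- **Aim II is secondary, and adjustment is expensive.** Also fair: a fall from 81% to 47% is a real loss. It is a reason to allow an exploratory label, not a reason to leave the status of the results undefined.

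Two stronger readings are tempting. One is that a false moderator is more likely than not. For the seven named variables that needs near-independent tests (51.2%), which is unlikely for two reports on the same child and for variables such as language, ethnicity and caregiver nativity. The other adds the Variable × Time terms, giving 28 tests and 1 − 0.95^28 = 76%. Those terms are prognostic and do not show which format suits whom, so that figure does not measure the harm at issue.

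**Conclusion.** The point holds. The plan assumes a study-wide family-wise rate of .05 but names no procedure or test family, and Aim II tests an open list of moderators on two informants with no defined threshold. At .05 per test, the chance of at least one false moderator is about 42% to 51% for the seven named variables on two informants, 30% on one informant, and about 52% to 64% for ten variables on two informants. All of these are far above .05.

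The figures rest on every moderator null being true, on an inferred threshold of .05, on assumed correlations and, for the last range, on an assumed count of ten. The documents do not support an unconditional claim that a false finding is more likely than not. The treatment comparison in Aim I is unaffected; what changes is how far Aim II results can be relied on.

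**What to change.** **Section 7.16.1.** Restrict the family-wise statement to the Aim I tests it is meant to cover, and say how it is met there, since no procedure is named for Aim I either.

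**Section 7.16.5.** Choose one of two routes before any outcome analysis by treatment arm.

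(a) *Controlled testing.* The sponsor fixes a closed list of moderators drawn from the domains in section 4.2. The seven variables in 7.16.5 are only examples, and nothing in the documents makes them the confirmatory set. Apply Holm (family-wise) or Benjamini-Hochberg (false discovery rate) across the three-way tests over both informants. Probe subgroups only where the adjusted p-value passes. Report other moderators as exploratory.

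(b) *Exploratory labelling.* Call Aim II exploratory, report every moderator tested with estimates and confidence intervals, and make no personalization claim from unadjusted significance.

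**Cost.** Either route is a change to the analysis text, with no change to data collection. Route (a) lowers power per moderator: at f = .068, from 81% to 47% under Bonferroni over 14 tests, with Holm or Benjamini-Hochberg losing less. Route (b) keeps the analyses as they are but limits what Aim II can conclude.

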8.1 Ethical Considerations

Recruitment and retention strategies: This study is designed as a pragmatic trial. To maximize external validity, CBT for child anxiety will be integrated into routine clinic workflows and all children ages 7-18 years, with exception of those meeting minimal exclusion criteria described below, will be eligible.

Retention strategies for CBT trial, data collection and follow-up assessments: Families will provide primary and additional contact information and will be provided with reminders for appointments and assessments. Modest patient incentives (\$25-50) over the course of study participation at each data point will be provided for completing assessments.

Exclusion Criteria: The intervention is suitable for patients ages 7-18 with elevated anxiety under consideration for outpatient psychological treatment. In this pragmatic trial, study entry criteria is very inclusive, so most anxious children with other problems are not excluded. However, children will not be able to participate if they are acutely at risk, if they require a higher level of care, or if they have developmental delays or intellectual impairments with very severe challenges (e.g., complete absence of verbal communication unrelated to anxiety).

Involvement of vulnerable populations: The study will recruit children between 7-18 years and a parent or legal guardian. It will not involve prisoners or institutionalized individuals. The study could involve four populations considered to be vulnerable: pregnant women, children, and non-English speakers. As detailed elsewhere, we will obtain informed consent, child assent where applicable based on the child's age, protect confidentiality, prevent undue influence and coercion, and protect against risks of the study.

- Pregnant women: Although the study will not specifically target pregnant women, given that the study enrolls young children and their families, it is possible that a participant could be pregnant. Such women will not be excluded. Women of childbearing potential will be entitled the same protections as listed above. We foresee no extra risk for a woman of childbearing potential relative to other participants.
- Children: This research targets youth with elevated anxiety. Parents between the ages of 16-21 who are the legal guardians of the child referred for assessment, will not be excluded based on age; thus it is possible that we will enroll parents who are under 21. Young parents often face additional barriers accessing health services for

their children. For this reason and because according to state law in the study jurisdictions, we plan to enroll parents in this age group. We have enrolled such parents in previous studies, which were reviewed and approved by the IRBs at each of our institutions and without any adverse events. Therefore, we are confident that protocols for the proposed research will be ethical, lawful and will be approved by the participating institutions' IRB.

- Non-English speakers: We include non-English speakers (Spanish speakers) in order to address the need for research and an evidence base for effective treatments in this population. All materials, modules, and general resources presented to participants will be available in Spanish. We will have Spanish speaking RAs conducting screening and assessments who will also be available to answer any questions participants have. Additionally, many of our therapists are Spanish speakers. We are confident that our study will have enough resources and staff available to Spanish speakers to ensure the ethical conduct of research.
- Children and Parents Involved with DCF: Children who are wards of the state will be excluded. Children who are involved with DCF will still require us to obtain informed consent from the legal guardian and permission from DCF prior to study enrollment. A caregiver confirmed to be safe by DCF must be available to voluntarily participate along with the youth as already outlined in the protocol for all youth/ family participants. We will not include study participants who are mandated to treatment. We will follow all applicable laws for including children and parents who are involved with DCF.

Research Sites: The settings for the proposed project are Academic Medical Centers and Community Health Centers. We will collect data from all of these sources via de-identified, coded data in REDCap.

Material to be collected. The study will not make any use of biological specimens. Investigators will gather data from the following sources: (1) Patient and family reported measures; (2) Semi-structured interviews; (3) Provider fidelity measures; (4) therapist engagement logs; (5) administrative data and patient records.

Access to individually identifiable private information. All research staff will complete CITI Human Subjects Training and Child Protection Training. Only study staff completing training in HIPAA regulations and human subjects protections will have access to study data. For all sources of data, with the exception of the interviews, all identifying information will be removed and names replaced by ID codes. Furthermore, identifying information will not be shared with others outside this study. Names and contact information for each participant will be stored in REDCap separate from project data. Project data will only be linked to the patient's record ID. For the interviews, only names, phone numbers, and site information will be available to the qualitative team to contact participants and conduct interviews.

Transcripts from interviews will be identified by ID codes and identifying personal information will be masked. Cross-reference listing of this contact information for the subset of interviewees will be kept in password-protected encrypted files on secure servers.

Data collection, management, and protection. Research Electronic Data Capture (REDCap) located at Boston Medical Center will securely collect research data from across all four study regions, and Boston Medical Center will be responsible for overseeing the integrity and security of the data. REDCap is a scalable, web-based electronic data capture system that allows the investigative team to build online surveys and databases and input remote data over a secure web connection (a SSL certificate is required). REDCap features *authentication, auto-logout setting, data logging* (audit trails for tracking data manipulation and export procedures), *user privileges* (each user only has access to granted projects; privileges are granular on the project level, e.g., being able to export, enter, add or modify database metadata, to build/run reports, to modify user privileges, to view logs, etc). REDCap can be used to collect data for 21 CFR Part 11, FISMA, and HIPAA-compliant environments, and is specifically geared to support online or offline data capture for research and operations. The Data Services Group of the FIU Center for Children and Families (CCF) will have continuous 24/7 access to the data as well as project administration rights in order to fully execute their duties of data management, monitoring, and analysis.

Planning, configuration and end-user support for REDCap will be provided by BU and the Data Services Group of the CCF. To help protect and secure the data stored in REDCap's database, the software application employs several methods to protect against malicious users who may attempt to identify and exploit any security vulnerabilities in the system. Access to the REDCap data entry website will be based on permissions granted by username and password which will be managed by the Boston University Clinical and Translational Sciences Institute for the Medical Campus Office of Information Technology. Only authorized study members will be able to enter or view data. The login information (username) of the person submitting the information, the date and time submitted, and other navigational information will be automatically obtained and stored in the database. Information posted on forms will be electronically encrypted using secure socket layering (SSL) encryption technology so that only the intended recipient can decode the data. Data will reside on a secure, password protected server at Boston Medical Center (BMC) to which only designated individuals have access, thus providing a secure environment for all project data. The database will be automatically backed up on a nightly basis. Files stored on BMC servers will be protected by electronic 'firewalls' that restrict access to designated users. Restrictions and permissions to update the database will be controlled through the REDCap web application.

Non-BMC sites will be able to access the REDCap system after submitting an end user agreement. A Boston University REDCap account will be created for them and the BMC team will be responsible for giving users a customized level of project access. In particular, the Data Services Group of the FIU Center for Children and Families (CCF) will have accounts created for them and will have continuous 24/7 access to the data as well as project administration rights in order to fully execute their duties of data management, monitoring, and analysis.

